**Mobile-enhanced group cognitive behavioral therapy for adolescents
with severe mood disorders**

**PI: [name]
UCLA Semel Institute for Neuroscience and Human Behavior**

NCT04887155

01/10/2021

Study Protocol

Overview of Study

Human Subjects Involvement, Characteristics and Design

Aim 1 involves two sets of human subjects: (1) a focus group (N=8 youth-parent dyads) with individuals who participated in the piloting of the transdiagnostic group treatment for youth at-risk for serious mental illness (SMD); (2) an open trial (N = 12 youth) testing the acceptability of the app-enhanced treatment for youth at high risk for SMD. Additionally, Aim 2 involves human subjects for the RCT (N=60) of the app-enhanced treatment and analysis of the results from this trial. Participants for Aim 1's focus will be recruited from a pool of participants previously enrolled in the pilot testing of our transdiagnostic treatment for youth at-risk for SMD and who consented to being contacted for future research. Participants for Aim 1's open trial and the RCT will be recruited primarily from UCLA's Child and Adolescent Mood Disorders Program (CHAMP). Additionally, flyers will be posted around the UCLA medical campus and within outpatient clinics throughout the hospital. Eligibility criteria is purposely broad to include as many youths at high risk for SMD as possible. Eligibility criteria is as follows:

Inclusion criteria:

1. Meet DSM-5 criteria for at least one past major depressive disorder, persistent depressive disorder, or unspecified bipolar disorder
2. Be 13-17 years old
3. English speaking and able to complete written questionnaires
4. Ability to attend pre-determined group session time(s)
5. Access to a smartphone to engage with the study app (open trial and RCT only)
6. Medication usage is acceptable, but not required

Exclusion criteria:

1. Regular use or current abuse of a psychoactive drug
2. Evidence of behavioral problems that are thought to interfere with group treatment
3. Suicidality that requires more intensive treatment
4. Meeting DSM 5 criteria for bipolar I or II disorder, a psychotic disorder, or significant psychiatric symptoms (e.g., self-injurious behavior) that require more intensive treatment
5. Concurrent participation in cognitive-behavioral therapy
6. Inability to travel to study sessions and assessments

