research outreach programs. I have budgeted in salary support for a research coordinator two days per week throughout Years 1-4 of the award. The research coordinator will screen all interested participants by phone to assess study eligibility, explain the purpose of the study and study procedures, and answer any questions. For individuals interested and eligible in participating, youth will complete the informed assent process and their parent/guardian will complete the informed consent process (detailed below). In addition to the phone screening of eligibility criteria, an in-person eligibility assessment will be conducted with the PI and research coordinator to assess for DSM/SIPS diagnostic criteria, explain the study procedures in more detail, and answer any questions. Recruitment will be done until there are enough participants to randomize and fill two groups of $n > 6$ per group.

Overview of study activities: Aim 1 will consist of focus groups, followed by an iterative app-development process with an interdisciplinary expert panel, and then an open trial of an app-enhanced cognitive-behavioral treatment (CBT). Focus groups will be held in a conference room at the UCLA Semel Institute and last approximately 60 minutes. The open trial will consist of a pre-treatment assessment, nine 90-minute group treatment sessions, and post-treatment session that includes an exit interview. Aims 2 & 3 will consist of a RCT of the app-enhanced CBT, which will compare nine 90-minutes sessions of the group CBT to nine 90-minute sessions of the app-enhanced group CBT. The RCT will also consist of a pre-treatment assessment, a post-treatment assessment, and a 3-month follow-up assessment following the completion of the group. The open trial and the RCT will be held in group therapy rooms at the UCLA Semel Institute. Finally, I will conduct longitudinal and machine learning analyses of data collected throughout the RCT.

Study Procedures, Materials, and Potential Risks

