Recruitment will start when an adolescent or their parent self-refers to the project or is referred by a treating physician or psychotherapist. When study candidates are referred by a mental health professional, this professional will give the participants a copy of an IRB-approved study flyer explaining the purposes and design of the study. The treating clinician can offer to contact the research team if the adolescent and at least one parent signs a HIPAA Authorization Form releasing their protected health information (names, diagnosis, ages, address, and telephone number) to the research team. This release will enable the team to contact the participants to determine their eligibility. A copy of the signed authorization form will be provided to the participants and placed in their medical chart. Alternatively, many families prefer to make the initial contact themselves rather than have their physician make the contact.

Telephone Screening, Informed Consent and Screening Visit

After referral to the program, the project coordinator will initiate a telephone interview of one or both parents of the adolescent. The coordinator will ask the parent to clarify the adolescent's reasons for referral to the program. If the adolescent and parents are interested and the adolescent appears eligible, they are invited to conduct a baseline eligibility assessment.

The initial baseline visit is intended for the adolescent and his or her primary caregiver(s). During this visit, we will obtain information on the presence of mood symptoms in the past month, past and current diagnoses and treatment for a psychiatric disorder and current medications and psychosocial treatments (if any). The project coordinator will explain the study protocol, answers all questions, and conducts the a semi-structured interview to determine eligibility. If the candidate is eligible, and the candidate and family wish to proceed, the project coordinator explains the written consent/assent documents to the parent(s) and adolescent. The coordinator will explain that, if the adolescent meets eligibility criteria the study offers treatment through a randomly assigned protocol involving either family psychoeducation and skills training or family psychoeducation and supportive individual treatment.

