treatment, is based on the premise that participants need to practice the skills in order to improve. Since participants commonly forget to do the skills, lose their homework assignments, or feel unmotivated to complete the skills, it challenges treatment developers to improve the current treatments and address these barriers to patient compliance. **We propose using a mobile app to improve patient compliance for youth at risk for SMD.** A mobile app can remind participants of skills they need to practice, provide the psychoeducation and skill-practice within the app, and provide contingencies that reward and increase motivation for skill-practice. Additionally, the large amounts of data that a mobile app collects allows for advanced statistical techniques, such as machine learning, to be applied. These efforts can provide a wide range of benefits to youth at risk for SMD and clinical science more broadly. Improving patient compliance can improve treatment outcomes, which reduces burdens on families who face these psychiatric challenges and society at-large who faces this emotional and financial burden. Additionally, through use of machine learning, we can better determine who will and who is benefitting from a skills-based treatment, like CBT. This prediction can help us better tailor treatment recommendations for patients and determine which patients will or will not benefit from a particular type of treatment.

STATISICAL DESIGN AND POWER

Power calculations

For this pilot RCT, we plan to randomize 60 participants to the randomized controlled-trial of the mobile-enhanced treatment. The two treatment groups will be randomized in a 1:1 ratio. Based on pilot trials of this treatment group as well as my primary mentor's ([name]) previous work with interventions for adolescents at high risk for SMI, we anticipate no more than 15-20% dropout by the end of the six-month study. Thus, we expect a final sample size of about 50 with full follow-up (25 in each treatment condition) across 3 assessment time-points (baseline, post-treatment, and three-month follow-up). Actual power will be higher as our general linear mixed modeling allows inclusion of data from subjects with partial data.

Additionally, data collected via the mobile application (app) should greatly increase the number of measurements.

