The remaining measures for treatment adherence (i.e., Homework Compliance Scale and Psychosocial Compliance Scale), as well as measures for app acceptability (i.e., Subjective App Usability Scale) and treatment acceptability (i.e., Subjective Treatment Acceptability) will be collected at the post-treatment assessment. Maintenance of treatment adherence will also be collected at the 3-month follow-up assessment. Treatments will be compared on these outcome measures using one-way analysis of variance (ANOVA).

- **Secondary analyses:** Treatment conditions will be compared using a general linear mixed modeling (GLMM) approach for secondary outcome variables (i.e., psychiatric functioning and psychosocial functioning) using IBM SPSS software. Time will be based on the standard interval assessments of the study – the baseline, post-treatment, and follow-up assessment). Time, treatment condition, and their interaction will be the primary predictors (controlling for any significant covariates). Psychiatric symptoms, psychosocial functioning, and emotion regulation (measured continuously) will be the outcome variables for these analyses.

We will also test a mediation analysis, with average participant adherence (measured throughout the study) as the mediator between treatment conditions and the secondary outcome variables. This will be done in two sets of analyses using the SPSS Process macros, which is a statistical package within SPSS that runs bootstrapped mediation analyses. First, the effect of treatment condition, mediated by average treatment adherence, on post-treatment psychiatric and psychosocial functioning will be examined. Second, the effect of treatment condition, mediated by average treatment adherence, on 3-month follow-up psychiatric and psychosocial functioning will be examined.

- **Exploratory analyses:** Two exploratory analyses will be examined. We will make use of the app's big data collection to begin to elucidate the app's effect on participant adherence and clinical outcomes.

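### The machine-learning analysis cannot show who benefits from CBT, because every randomised youth receives group CBT; it can predict only outcome under group CBT

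*Combined protocol and SAP*

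**What the plan says.** All references are to the combined protocol and SAP.

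- **Purpose.** Knowledge Gained (under Importance of the Knowledge to be Gained) states that "through use of machine learning, we can better determine who will and who is benefitting from a skills-based treatment, like CBT". It adds that the prediction can help tailor recommendations and "determine which patients will or will not benefit from a particular type of treatment".
- **Data.** Overview of study activities commits to the analysis: "I will conduct longitudinal and machine learning analyses of data collected throughout the RCT".
- **Arms.** The same paragraph describes the RCT as one "which will compare nine 90-minutes sessions of the group CBT to nine 90-minute sessions of the app-enhanced group CBT". The only other treated sample is "an open trial (N = 12 youth) testing the acceptability of the app-enhanced treatment for youth at high risk for SMD", a single arm that also receives the app-enhanced treatment.
- **Analysis plan.** Statistical analyses gives no machine-learning outcome, predictors, model, validation or arm-by-predictor contrast. It says "Two exploratory analyses will be examined"; these concern adherence trajectories and app use.
- **Limits stated.** Power calculations says that the pilot does not set out to assess efficacy formally or to estimate effect size.
- **A conflicting description.** Telephone Screening, Informed Consent and Screening Visit has the coordinator describe a "randomly assigned protocol involving either family psychoeducation and skills training or family psychoeducation and supportive individual treatment". This does not match the arms in the Overview.

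**The concern.** Benefit from CBT means outcome with CBT minus the outcome the same kind of youth would have had without it. The second term is not observed for any participant or subgroup in this design. More app data or a better algorithm does not supply it.

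The gap matters in this population. Youths can enter on a past mood diagnosis, may be taking medication, and may take up ancillary treatment during the study. Considerable movement in symptoms can be expected whatever CBT does. A model that predicts this movement well may look like a tool for choosing treatment. If its output were read that way, youths who would have improved anyway could be labelled CBT responders, and youths who were mild at entry and had little room to improve could be labelled non-responders. The pilot is meant to inform a larger grant application, so the reading could be carried forward.

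**Working it through.** The plan gives no figure for the machine-learning analysis. Its 80% power statement concerns the group-by-time interaction and is not used here.

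**Inputs from Power calculations:** 60 randomised 1:1; 15–20% dropout; about 50 completers (60 × 0.85 = 51, 60 × 0.80 = 48), 25 per arm; two-sided alpha .05; within-subject correlation r = .5.

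**Step 1. Can the data distinguish different CBT effects?** Let x be a standardised baseline predictor and let the outcome under CBT be 0.5x − 0.5 plus noise with variance 0.75. The coefficients are assumptions. Three scenarios give this same outcome distribution:

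| Scenario | Course without CBT | CBT benefit | Mean R² (N=50, 4,000 runs) | Correlation of prediction with true CBT benefit |
|---|---|---|---|---|
| A | 0.5x − 0.5 | 0 | 0.257 | undefined (no benefit) |
| B | 0 | 0.5x − 0.5 | 0.256 | +1 |
| C | 1.0x − 0.5 | −0.5x | 0.256 | −1 |

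Predictive accuracy is the same whether CBT benefit is absent, fully predicted, or predicted in reverse. The app-by-predictor coefficient averages about 0 in all three, so the randomised contrast does not tell them apart either.

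**Step 2. How good could a model look with no CBT effect?** Let B and P be baseline and post-treatment severity with equal variances (assumed), correlation r, and improvement B − P.

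- corr(B, B − P) = (1 − r)/√(2(1 − r)) = √((1 − r)/2). At r = .5 this is √.25 = .50, so baseline explains 25% of the variance in change (35% at r = .3, 15% at r = .7).
- Mean improvement in the more severe half is (1 − r)√(2/π) = .5 × .798 = 0.40 SD. The milder half worsens by 0.40 SD.
- The AUC of B for above-median improvement, from 2,000,000 simulated draws, is .73 at r = .5, .77 at r = .3 and .68 at r = .7.

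**Step 3. What can the randomised contrast support?** It can address who gains from adding the app. For a balanced binary predictor crossed with arm, with N/4 per cell and outcome SD 1:

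- SE of the interaction = 4/√N = 4/√50 = 0.566.
- Detectable at 80% power: (1.960 + 0.842) × 0.566 = 1.58 SD. With all 60 participants it is 1.45 SD.
- Power at N = 50 for 0.5 SD: Φ(0.5/0.566 − 1.960) = Φ(−1.08) = 14%. For 0.8 SD: Φ(1.41 − 1.96) = 29%.

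**The case against.** Four points can be made for the plan.

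- *The sentence is aspirational rationale, not a specified estimand.* This stands in part. The text says what machine learning can do. The analysis section defines no such estimand, and it covers Aims 1 and 2 although the Overview mentions Aim 3. The Research Strategy that the text refers to is not among the documents. But the Overview makes machine learning a planned activity, Knowledge Gained is the only place that states its purpose, and nothing elsewhere corrects it.
- *The plan already disclaims efficacy.* It does, and this makes it less likely that recommendations would be issued straight from this trial. It does not retract the claim about individual benefit. A study that will not estimate average efficacy is not well placed to support patient-level treatment choice.
- *A type of treatment could mean app-enhanced CBT.* For that a randomised contrast exists, and some benefit question is identifiable. The preceding sentence, however, names CBT itself.
- *The AUC belongs to an assumed model.* This stands. The change score, the baseline-severity predictor, the median split and equal variances are not in the plan, and r = .5 is a power-calculation assumption. The plan ties machine learning to app data rather than to baseline severity alone. The figure shows what could happen; it does not measure a defect.

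A reader might infer that the model would capture nothing but natural remission and regression to the mean. The documents do not support that: outcome under CBT also contains whatever effect CBT has, which simply cannot be isolated.

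**Conclusion.** The claim to determine who benefits from CBT, and thereby to guide treatment choice, is not supported by the design. This follows from the arms described in the Overview and needs no numerical assumption. The most the model can deliver is a prediction of outcome under group CBT, with or without the app.

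The AUC of about .73 is illustrative and rests on the assumptions in the working. The benefit question that randomisation does open, app versus no app, is identifiable but very weakly powered: 80% only at about 1.58 SD, and 14% at 0.5 SD, under a normal approximation with 50 completers and a balanced binary predictor.

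A reader might go further and take this as a flaw in the trial's main analyses. It is not: the adherence comparison, the secondary mixed models, the mediation analysis and the two listed exploratory analyses do not depend on this sentence.

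The arms given in the telephone-screening section must be reconciled with the Overview. That text names no untreated arm, and neither of its arms is described as the group CBT under study, so as it stands it does not rescue the claim.

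**What to change.** 1. In Knowledge Gained, restate the purpose and conclusion of the machine learning as predicting post-treatment and 3-month status among youths receiving group CBT with or without the app (prognosis). Delete the claim to determine who benefits from CBT or to guide treatment choice.
2. Confine any statement about benefit to the randomised app versus no-app contrast, through arm-by-baseline-predictor terms that use predictors collected alike in both arms. Label it hypothesis-generating and report its low power with the figures above.
3. Reconcile the description of the arms in the telephone-screening section with the Overview.

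**Cost.** Item 1 is wording. Item 2 needs a short new specification (outcome, time point, predictors), because Statistical analyses contains no machine-learning model to amend. No new data are required. The stated claim becomes less ambitious. App-only data, which the plan gives as its reason for machine learning, cannot enter the benefit contrast; they remain usable for prediction within the app arm, at about 25 completers.

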The power calculation assumes a two-sided significance level, $\alpha=.05$, and a within-subject correlation of $r=.5$ between repeated measures. Under these calculations, for outcomes measures at the three primary assessment time-points, we have 80% power to detect an overall group by time interaction corresponding to a differential treatment effect across the two study arms with an effect size of $f=.30$, just above the above Cohen's threshold for a medium effect ($f=.25$). Thus, recruiting 60 participants will provide ample data for this pilot RCT in order for us to determine initial clinical meaningfulness for the larger grant application to follow this study. However, in accordance with NIMH guidance on the role of pilot RCTs (see: <https://grants.nih.gov/grants/guide/rfa-files/RFA-MH-18-706.html>), this study does not propose to formally assess clinical efficacy or estimates of effect size, due to the unreliability of estimates and limited statistical power yielded from pilot studies.

Statistical analyses

Aim 1 – App acceptability:

- Open trial acceptability: Following the open-trial, we will score participants' rating of app acceptability and treatment satisfaction and burden. We expect high ratings of acceptability (scores>4/5) for the treatment and the app. We will also calculate participant adherence via the extent of weekly practice and percentage of weekly skills practiced. We expect the percentage of weekly skills practiced to be greater than our pilot study as well as the average homework adherence in the literature (>50%).

Aim 2 – Pilot RCT of App-UP:

- Primary Analyses: Treatment conditions will be compared using a general linear mixed modeling (GLMM) approach for the weekly measurements of treatment adherence (both self-report and clinician rated measures) using IBM SPSS software. Time will be based on the standard interval assessments of the study – the baseline, post-treatment, and follow-up assessment). Time, treatment condition, and their interaction will be the primary predictors (controlling for any significant covariates).

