 1. Using functional data analytic techniques, the uptake of that app will be examined. First, each of the components of participant adherence (skill-practice, symptom monitoring, and review of session content) will be examined to determine the functional pattern of participant adherence over time. This analysis will examine the trajectories of each component of participant adherence over the study to examine their function (i.e., increasing, decreasing, stable over time). Additionally, this analysis will determine which component of participant adherence had the highest frequency of practice.
 2. The frequency and duration of app use will be mapped across the study to determine how often and for how long participants engaged with the app. Additionally, the frequency and duration of app use will be moderated with time of reward reinforcement to determine if the use of the app was affected by the reward structures (e.g., leveling up, receipt of an emoji) within the app.

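### The primary Aim 2 model analyses weekly adherence on a three-assessment Time axis that gives the weekly values no defined place, and no primary between-arm contrast is named for it

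*Combined protocol and SAP*

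**What the plan says.** All references are to the combined protocol and SAP.

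- **Statistical analyses, Aim 2, Primary Analyses.** The arms are compared by a mixed modelling "approach for the weekly measurements of treatment adherence (both self-report and clinician rated measures) using IBM SPSS software". The next sentence says "Time will be based on the standard interval assessments of the study" and lists baseline, post-treatment and follow-up. Then: "Time, treatment condition, and their interaction will be the primary predictors".
- **Same section, next paragraph.** The remaining adherence scales, and the app and treatment acceptability scales, are collected at post-treatment. "Maintenance of treatment adherence will also be collected at the 3-month follow-up assessment". These measures are compared by one-way ANOVA.
- **Secondary analyses.** The same Time sentence is used for psychiatric symptoms, psychosocial functioning and emotion regulation. Average adherence over the study appears here as a mediator.
- **Exploratory analyses, item 1.** Adherence is broken into skill practice, symptom monitoring and review of session content, and its trajectory is described by functional data analysis.
- **Power calculations.** The plan expects that "data collected via the mobile application (app) should greatly increase the number of measurements". The power statement is that "for outcomes measures at the three primary assessment time-points, we have 80% power to detect an overall group by time interaction". The section closes by saying that the pilot does not formally assess efficacy or effect size.

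**The concern.** The outcome and the Time variable of the primary model do not fit each other. A value from, say, the fourth week of treatment is neither a baseline, a post-treatment nor a follow-up value. The plan does not say whether it is averaged, assigned to the nearest assessment or left out. No baseline adherence measure is described either. The same Time sentence fits the secondary outcomes, so it looks like wording carried over from there.

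The second gap is the test. Three model terms share primary status. The only pointer to a particular one is the group by time interaction in the power statement, and that is limited to outcomes at the three assessments. The plan also does not say whether the self-report or the clinician-rated weekly measure leads.

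Adherence is what the app is meant to change, and this comparison is labelled primary. Two analysts following the text could choose different axes, terms and measures and report different primary adherence results. The choice could also be made with the data in view.

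**Working it through.** **1. Outcome against axis.**

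| Item | Primary Analyses | Secondary analyses |
|---|---|---|
| Outcome | weekly adherence | symptoms, functioning, emotion regulation |
| Time levels | baseline, post-treatment, follow-up | the same three |
| Do the weekly values have a level? | not between baseline and post-treatment | not applicable |
| Mapping or pooling rule | none | none needed |

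Average adherence is defined only as a mediator, and trajectories over the study are exploratory. Neither supplies the rule that the primary model lacks.

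**2. The plan's own power figure.** It is 80% for the interaction at f = .30, r = .5, two-sided alpha .05, three assessments and about 50 participants with full follow-up. With a noncentral F on 2 and 96 df, the result depends on how f is defined:

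| Noncentrality λ | Value | Power |
|---|---|---|
| f²·N·3/(1−r) | 27.0 | 99.8% |
| f²·N·3 | 13.5 | 91.0% |
| f²·N·2 | 9.0 | 75.7% |
| f²·(N−2)·2 | 8.64 | 73.8% |
| f²·N | 4.5 | 44.8% |

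None gives 80%. The plan does not state its definition of f, so this alone does not show the figure to be wrong. The present point does not depend on it, because the statement does not cover weekly values.

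**3. Why the contrast must be named along with a weekly axis.** From the documents: n = 25 per arm and alpha .05 two-sided (Power calculations), and r = .5, carried over from the three-assessment calculation. Assumed: k = 9 weekly values (one for each of the nine sessions in Overview of study activities), unit SD, equal correlation between weeks, independent participants.

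*Difference in mean weekly adherence, constant gap of 0.6 SD.*
- Variance of a person's mean = (1 + (k−1)r)/k = (1 + 8 × .5)/9 = .556, so SD = .745.
- Standard error of the difference = .745 × √(2/25) = .211.
- Noncentrality = .6/.211 = 2.85; noncentral t, 48 df: **79.6%**.
- Six values give 77.7% and twelve give 80.6%. With nine values, r = .3 gives 92.2% and r = .7 gives 68.0%. At r = .5, a gap of 0.5 SD gives 64.2% and 0.7 SD gives 90.2%.

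*Condition-by-week interaction.*
- λ = (n/2) × Σ(gap − mean gap)²/(1−r).
- Constant gap: the sum is 0, so power equals alpha, **5%**.
- Gap widening evenly from 0.3 to 0.9 SD (mean 0.6): steps of .075, sum = .075² × 60 = .3375, λ = 12.5 × .3375/.5 = 8.44.
- Week as nine categories (8 and 384 df): **49.2%**.
- Week as a linear term: **81.2%** with 48 df, **82.6%** with 392 df.
- A gap fading from 0.9 to 0.3 SD gives the same figures, so a significant interaction alone does not show that the app helps.

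A simulation of 20,000 trials gave 79.2% for the mean contrast. For the linear interaction it gave 5.1% (constant gap) and 81.5% (0.3 to 0.9 SD).

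**4. Clustering.** Treatment is given in groups. With an assumed intraclass correlation of .05 and groups of 6 to 8, the design effect is 1 + 5 × .05 = 1.25 to 1 + 7 × .05 = 1.35. The 79.6% then falls to about 70% to 67%.

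**The case against.** *The 5% is not a fault of the current plan.* This stands. The plan has no condition-by-week term. A reader might infer that the present text would miss a steady benefit, but the documents do not support that, because the plan's axis includes baseline. If a baseline adherence value existed and the gaps were 0, 0.6 and 0.6 SD, then λ = 12.5 × .24/.5 = 6.0, and the interaction (2 and 96 df) would have about 57% power. With gaps of 0, 0.6 and 0.3 SD, λ = 4.5 and power is about 45%.

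*The post-treatment and follow-up levels may hold data.* This also stands. It is tempting to infer that those levels are empty because adherence at those visits goes to ANOVA. But the ANOVA paragraph covers the remaining scales and 3-month maintenance. It does not show that the weekly measures lack a value near post-treatment. Nor do the documents suggest an intention to discard weekly data, since adherence over the study is used elsewhere.

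*A mixed model accepts several observations per level, and basing Time on the assessments could mean grouping weeks by interval.* That is possible, but it is itself a pooling rule, and none is given. The absence of a described baseline measure is weaker evidence, because the document has no full schedule of measures. Review of session content plainly cannot precede the first session; the other two adherence components might.

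*The mean over weeks is a preference.* This is partly right. It is a suitable choice, and a linear interaction can match it. What needs correcting is the undefined axis and the unnamed contrast.

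*This is a pilot.* That lowers the stakes but does not make the model specification workable.

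**Conclusion.** The point holds and should be fixed. The Time definition does not fit the weekly outcome it is applied to, so the text is wrong as written and not merely short of detail. As it stands, the model cannot be fitted to the weekly values without an unstated reduction of them. No primary between-arm contrast is named for weekly adherence, because the group by time interaction in the power statement is confined to the three-assessment outcomes.

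This conclusion rests on the text alone. The power figures only show why a new axis and a named contrast must come together. With week as the axis and a constant 0.6 SD benefit, the mean contrast has about 80% power (68% to 92% over r = .7 to .3) and the interaction 5%. With a gap widening from 0.3 to 0.9 SD, the interaction has 49% or 81% to 83%, depending on whether week is categorical or linear. The number of weeks, the equal correlation, the independence of participants and the effect sizes are assumptions, and clustering by therapy group would lower the figures. The stakes are moderate: no confirmatory decision depends on this test.

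**What to change.** Before any outcome data are seen, amend Primary Analyses as follows:

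1. For weekly adherence, replace the three-level Time variable with treatment week, and state how many weeks are recorded. Keep the three assessments as Time for the secondary outcomes only.
2. Name one primary between-arm contrast. The difference in mean weekly adherence over the treatment period is suitable because it captures a steady benefit; condition-by-week can be the secondary trajectory test.
3. State whether week is categorical or linear.
4. State whether the self-report or the clinician-rated weekly measure leads.
5. Analyse 3-month maintenance separately, as the plan already does.
6. Label the power statement as applying to the three-assessment outcomes.

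The cost is a few sentences, with no new data, visits or participants. The downside is that the chosen contrast may differ from the interaction in the power statement, and that if the gap changes steeply over weeks a linear interaction can match or exceed its power.
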